6.3 Dose modifications

6.3.1 Dose modification and dose interruption

For patients who do not tolerate the protocol-specified dosing schedule, dose interruptions are mandated in order to allow patients to continue study treatment. Dose interruption for PDR001 includes delaying or withholding treatment for any reason as well as interrupting treatment during an infusion.

The following sections address specific instructions for mandatory dose modifications and recommended management of adverse events considered suspected to be related to PDR001.

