Based on literature from compounds with similar mechanism of action of PDR001, instructions have been developed regarding how to identify, assess severity and manage irAEs that may occur in patients receiving PDR001. The dose modification requirements and AE management guidelines for the potential irAEs are provided in the following tables: diarrhea/colitis ([Table 6-2](#)), hepatitis (liver laboratory alterations) ([Table 6-3](#)), skin (rash) ([Table 6-4](#)), nephritis ([Table 6-5](#)), pneumonitis ([Table 6-6](#)), encephalitis ([Table 6-7](#)), endocrinopathies ([Table 6-8](#)), PDR001-infusion reaction & cytokine release syndrome ([Table 6-9](#)), and other potential immune-related AEs of special interest ([Table 6-10](#)). Any grade 4 irAE must result in permanent discontinuation of PDR001.

Under the category of OTHERS ([Table 6-11](#) and [Table 6-12](#)) are included several irAE of interest that must be managed specifically and for which not specific guidance are provided in the table below. OTHERS include (but is not restricted to) the following events: autoimmune neuropathy, demyelinating polyneuropathy, Guillain-Barre, myasthenia Gravis-like syndrome, non-infectious myocarditis, non-infectious pericarditis, pancreatitis and rapid onset of grade 3 fatigue in the absence of disease progression.

Patients receiving PDR001 may experience irAEs other than those listed in this document; therefore, all AEs of unknown etiology associated with drug exposure should be evaluated to determine if they are possibly immune-related. In cases where the specific irAEs are not listed in the tables below, the investigator should follow the dose modification requirements in [Section 6.3.1.3](#) which details the measures to be taken for suspected (they could be potentially immune-related or non-immune-related) AEs. Investigators are encouraged to contact the sponsor as needed to discuss cases that warrant separate discussion outside of the scope of the current instructions.

The dosing modification requirements are mandatory; however, the AE management guidelines are recommendations and can be modified according to local practices. The management of irAEs may include initiation of antibiotics for prophylaxis against opportunistic infections.

Table 6-2 Mandatory dose modification requirements and recommended clinical management guidelines for potential immune-related diarrhea/colitis

Diarrhea/Colitis (NCI-CTCAE v4.03)		

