Grade	Recommended Adverse Event management guidelines	Mandatory Dose Modification requirements
Grade 1 (< 4 bowel actions per day over baseline) mild Grade 2 (4-6 bowel actions per day over baseline) and / or abdominal pain/ blood in stool.	
 ● Diet ● Hydration ● Loperamide: initially 4 mg, followed by 2 mg every four hours or after every unformed stool; maximum 16 mg/day. Continue until diarrhea free for 12 hours; ● Diarrhea > 24h: loperamide 2 mg every two hours; maximum 16 mg/day. Consider adding oral antibiotics. ● Diarrhea > 48hrs: loperamide 2 mg every two hours; maximum 16 mg/day. Consider other second-line therapies for diarrhea (e.g: (octreotide, oral diphenoxylate) and oral antibiotics ● If Grade 2 and no improvement in 5 days may require oral steroids ● If Grade 2 diarrhea persists >1 week consider GI consultation and endoscopy to evaluate for colitis. ● If Grade 2 persists for 5 days and worsening of symptoms or diffuse ulcerations and bleeding seen on endoscopy, commence steroids at a dose of 0.5-1mg/kg per day of prednisolone (or IV equivalent) and continue until symptoms improve to Grade 1. If no improvement occurs, manage as per Grade 3. Steroids can be tapered as per Section 6.3.1.2.2. ● Sigmoidoscopy and biopsy can be considered and may assist in determining the duration of steroid taper based on the evidence of macroscopic and microscopic inflammation. 	
 ● Continue PDR001 treatment ● If diarrhea is Grade 2, despite loperamide at 2 mg every two hours for > 48hrs: 
 ● Interrupt PDR001 until diarrhea recovers to Grade ≤1 and then restart PDR001 treatment at the same dose and schedule.

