Grade 1: Rash covering < 10% Body Surface Area (BSA)	
 ● Initiate prophylactic and symptomatic treatment measures. ● Consider use of topical corticosteroids or urea containing creams in combination with oral antipruritics or moderate strength topical steroid (hydrocortisone 2.5% cream or fluticasone propionate 0.5% cream) ● Reassess after 2 weeks. 	Continue PDR001 treatment
Grade 2: 10-30% of BSA	
 ● If tolerable, treat as per Grade 1; ● If intolerable, initiate systemic steroids (e.g. oral prednisolone 0.5-1mg/kg daily) and consider dose interruption until tolerable or recovery to grade ≤1 or baseline; once recovered, resume PDR001 treatment at the same dose and schedule. ● If symptoms persist or recur consider skin biopsy. 	
Continue PDR001 treatment
 
AE resolution to ≤1 or baseline must occur within a period of 12 weeks since Grade 2 event has been identified, otherwise PDR001 must be permanently discontinued.

Grade 3: More than 30% of BSA	
 ● Obtain a skin biopsy and dermatology consult. ● Initiate systemic steroids with 1mg/kg of prednisolone or IV equivalent. 	
1st occurrence:
 
 ● Interrupt PDR001 until rash recovers to Grade ≤1 or baseline ● Once recovered restart PDR001 treatment at the same dose and schedule 
AE resolution to ≤ Grade 1 or baseline must occur within a period of 12 weeks since intolerable Grade 3 event has been identified. Otherwise, PDR001 must be permanently discontinued
 
2nd occurrence: Permanently discontinue PDR001

Grade 4: Life-threatening	Same as Grade 3	Permanently discontinue PDR001
Other skin events		
Stevens-Johnson syndrome and toxic epidermal necrolysis	Institute supportive care as per institutional guidelines	Permanently discontinue PDR001

Table 6-5 Mandatory dose modification requirements and recommended clinical management guidelines for potential immune-related nephritis

Nephritis (NCI-CTCAE v4.03)		
Grade	Recommended Adverse Event management guidelines	Mandatory Dose Modification requirements
Grade 1: Creatinine >ULN to ≤1.5x ULN)	
 • Monitor creatinine weekly • If creatinine return to baseline resume routine creatinine monitoring per protocol • Promote hydration and cessation of nephrotoxic drugs 	Continue PDR001 treatment

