6.4.3 Prohibited concomitant therapy

During the course of the study, patients must not receive other additional investigational drugs, devices, chemotherapy, or any other therapies that may be active against cancer or modulate the immune responses. However, limited-field palliative radiotherapy may be allowed as concomitant therapy. Such local therapies administered during the study treatment must be entered into the CRF. Additionally, no other therapeutic monoclonal antibodies and no immunosuppressive medication may be administered while on this study unless given for the management of immune toxicity.

The use of somatostatin analogs or any other medications administered to control active symptoms related to carcinoid syndrome is not permitted during the study unless there is a change to functional status (Section 6.4.4.1).

The use of systemic steroid therapy and other immunosuppressive drugs is not allowed except for the treatment of infusion reaction, irAEs, and for prophylaxis against imaging contrast dye allergy or replacement-dose steroids in the setting of adrenal insufficiency (providing this is < 10 mg/day prednisone or equivalent), or transient exacerbations of other underlying diseases such as COPD requiring treatment for \leq 3 weeks. If systemic corticosteroids are required for the control of infusion reactions or irAEs, it must be tapered and be at non-immunosuppressive doses (< 10 mg/day of prednisone or equivalent) before the next administration of study treatment. If the dose of prednisone or equivalent cannot be reduced to less than 10 mg/day before the administration of next dose of study treatment then PDR001 must be discontinued.

The use of live vaccines is not allowed through the whole duration of the study. Inactivated vaccines are allowed.

There are no prohibited therapies during the post-treatment follow-up period.

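### Table 6-4 gives intolerable Grade 2 rash a binding instruction to continue PDR001 and, in the same row, a non-binding suggestion to consider interrupting it; the two need reconciling.

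*Protocol*

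**What the plan says.** The Grade 2 row of Table 6-4 (rash over 10-30% of body surface) has two cells that matter here.

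- **Mandatory dosing cell:** "Continue PDR001 treatment". It adds one condition: "AE resolution to ≤1 or baseline must occur within a period of 12 weeks since Grade 2 event has been identified", failing which PDR001 stops permanently. It draws no line between tolerable and intolerable rash and has no interruption branch.
- **Recommended management cell:** this does split by tolerability. Tolerable rash is handled as Grade 1. Otherwise: "If intolerable, initiate systemic steroids (e.g. oral prednisolone 0.5-1mg/kg daily) and consider dose interruption until tolerable or recovery to grade ≤1 or baseline", with PDR001 resumed after recovery.

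Section 6.3.1.2.1 ranks the columns: "The dosing modification requirements are mandatory; however, the AE management guidelines are recommendations and can be modified according to local practices".

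Three other places bear on the same patient.

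- Section 6.3.1 states: "For patients who do not tolerate the protocol-specified dosing schedule, dose interruptions are mandated in order to allow patients to continue study treatment".
- Section 6.1.1 allows a dose to be interrupted for up to 12 weeks, without tying this to a particular event.
- Section 6.4.3 says of systemic corticosteroids given for immune-related events that "it must be tapered and be at non-immunosuppressive doses (< 10 mg/day of prednisone or equivalent) before the next administration of study treatment". If that level cannot be reached before the next dose, PDR001 must be discontinued.

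**The concern.** A site treating a patient with intolerable Grade 2 rash finds a binding cell that says carry on and a non-binding cell that says start steroids and think about stopping for a while. Neither cell refers to the other. Some sites may dose through the rash and others may withhold, each with text to point to.

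Skin events are adverse events of special interest (protocol Section 8.1.3), and Section 12 permits no authorized deviations, so a site that interrupts could be recorded as deviating from a mandatory requirement. The outputs affected are:

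- dose interruptions and their reasons, which serve as the tolerability measure (protocol Section 10.5.3.6, SAP Section 2.4.1);
- special-interest events leading to interruption (SAP Section 2.8.1.1);
- protocol deviations (SAP Section 2.3.1).

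Dosing continues for some patients after the primary cut-off, so the row remains in use.

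**Working it through.** **The text, side by side.** The plan states no figure on this point, so the main check is a comparison of passages.

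1. The dosing cell covers all of Grade 2, and the management cell carves out the intolerable cases. The two diverge only for those cases.
2. Section 6.3.1.2.1 gives the dosing cell priority. On a literal reading, the instruction to continue outranks the suggestion to interrupt.
3. Other rows place such a branch in the binding column. For persistent Grade 2 diarrhea, the mandatory column of Table 6-2 says: "Interrupt PDR001 until diarrhea recovers to Grade ≤1 and then restart PDR001 treatment at the same dose and schedule". Table 6-12 groups intolerable Grade 2 with Grade 3 in a separate row whose mandatory cell requires interruption.
4. Rash does not default to Table 6-12, because Section 6.3.1.3 reserves that table for events without specific requirements elsewhere.
5. The Grade 3 dosing cell of Table 6-4 starts its 12-week clock from an intolerable Grade 3 event, although Grade 3 has no tolerability split. This suggests, without proving, that tolerability wording was misplaced within the table.

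**Does the row's steroid fit with continuing on schedule?** Inputs:

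- steroid dose 0.5-1 mg/kg (Table 6-4, given as an example);
- body weight 70 kg (an assumption), with 30-150 kg as the range in Section 2.3;
- taper of 2.5-5 mg every 3-7 days (Section 6.3.1.2.2);
- dose to be below 10 mg/day before the next infusion (Section 6.4.3);
- infusions every 28 days with a window of 7 days either side (Section 6.1.1), so at latest 28 + 7 = 35 days after the previous one.

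Starting dose = weight × mg/kg: 70 × 0.5 = 35 mg and 70 × 1 = 70 mg.

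Number of steps = the smallest n for which start − n × decrement < 10. Days = n × interval.

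| Start | Fastest (5 mg every 3 days) | Slowest (2.5 mg every 7 days) |
|---|---|---|
| 35 mg | 6 × 3 = 18 days | 11 × 7 = 77 days |
| 70 mg | 13 × 3 = 39 days | 25 × 7 = 175 days |

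Only the 35 mg start at the fastest rate fits within a cycle. Even then, steroids must begin no later than 35 − 18 = 17 days after the last infusion. From 70 mg, the fastest taper (39 days) already overruns 35 days.

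Over 30-150 kg the starting dose is 15-150 mg/day, always above the limit. The time to get below 10 mg runs from 6 to 87 days at the fastest rate and from 21 to 399 days at the slowest. All figures assume that the taper starts at once; any period at full dose adds to them.

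**A related mismatch.** Section 6.3.1.2.2 allows restart once the taper reaches 10 mg/day, whereas Section 6.4.3 requires less than 10 mg/day. Stopping at exactly 10 mg needs one step fewer: 15-70 days from 35 mg and 36-168 days from 70 mg.

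**The case against.** The strongest reply is that this is an ambiguity and not an impossibility, and much of that stands.

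- A reader might infer that the binding cell forbids interruption and that sites cannot comply with both columns. The documents do not go that far. The dosing cell contains no express ban, the management cell asks only that interruption be considered, and Section 6.1.1 allows interruptions generally. A site that considers interrupting and then continues has followed both cells. The row could mean that no change is required and interruption is at the investigator's discretion. That reading is tenable, but the table does not state it, and Section 6.3.1.2.1 describes the dosing column as mandatory.
- Section 6.3.1 may settle the matter. If not tolerating the schedule includes an intolerable rash, interruption is already binding and the dosing cell governs only tolerable cases. If the phrase concerns the schedule and not a single event, it adds no conflict. The protocol does not say which, so a site cannot rely on it.
- A reader might infer that continuing can never be combined with the row's steroids. The 18-day result refutes that. The steroid dose is only an example in the non-binding column, and the Section 6.4.3 threshold applies to every immune-related event treated with systemic steroids.
- A reader might assume that the event is common. Section 1.2.1.2 reports suspected rash in 3 of 32 patients in one study and maculo-papular rash in 4 of 18 in another. Rash is not listed among suspected events at 5% or more in the 160-patient study, or among events at 15% or more in this trial's interim analysis. None of these figures isolates intolerable Grade 2 rash.
- Interruptions and their reasons are recorded, so differing site practice would be partly visible in the data.

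**Conclusion.** The inconsistency is real but limited. For intolerable Grade 2 rash, the binding cell taken literally conflicts with the interruption suggested beside it and does not fit with Section 6.3.1. A discretionary reading is available but unstated.

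The row's example steroid dose often, though not always, prevents an on-schedule infusion under Section 6.4.3. At an assumed 70 kg, three of the four corner cases exceed the 35-day limit, and the fourth fits only if steroids start early enough in the cycle. This makes the choice of reading matter. If no interruption is allowed, a patient still at 10 mg/day or more when the next dose falls due is pointed towards discontinuation by Section 6.4.3. If one is allowed, the taper can finish and dosing can resume.

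The textual conflict rests on no assumption. The durations rest on the assumed weight, the example dose and an immediate taper. How many patients are affected cannot be derived from the documents. What is at stake is patient safety and the interruption, deviation and exposure data; no effect on the response-rate endpoint is claimed.

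**What to change.** Reconcile the two cells of the Grade 2 row in Table 6-4 with each other and with Sections 6.1.1, 6.3.1, 6.3.1.2.1, 6.3.1.2.2 and 6.4.3. Intolerable Grade 2 rash should have one binding dosing instruction, placed in the mandatory column and consistent with the steroid condition for redosing. If interruption is meant to be discretionary, that column should say so. The restart level of 10 mg/day in Section 6.3.1.2.2 and the below-10 mg/day condition in Section 6.4.3 should be aligned in the same edit. Which instruction and which threshold apply is for the clinical team; this point takes no position.

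The cost is wording in one table row plus the alignment of the cross-referenced sections. No change to the sample size, the endpoints or the SAP analyses is needed.

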6.1.1 Dosing regimen

Table 6-1 Dose and treatment schedule

Study treatments	Pharmaceutical form and route of administration	Strength	Frequency and/or Regimen	Dose Administered
PDR001	Powder for solution for infusion in vial for i.v. infusion	4 x 100 mg vials	Every 4 weeks	400 mg

PDR001 will be administered via intravenous infusion over 30 minutes (up to 2 hours, if clinically indicated) once every 4 weeks (+/- 7 days window). PDR001 will be administered on Day 1 of every cycle. Each cycle is 28 days. The actual date of Cycle Day 1 will be used to project the dates of future cycles. The dose may be interrupted for up to 12 weeks. The safety assessments (as per [Table 7-1](#) and [Section 7.2.2](#)) should be performed according to the actual day of infusion.

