6.3.1.1 Dose modification and dose interruption for PDR001

General dose modification instructions:

No changes in the dose of PDR001 are allowed.

AEs are to be graded according to NCI-CTCAE v4.03 (ctep.cancer.gov). All dose interruptions and the reasons for dose interruption must be documented in the eCRF.

Treatment of patients with AEs suspected to be related to PDR001 including those of potential immune-mediated etiology (irAE) (see definition in [Section 6.3.1.2.1](#)) must be permanently discontinued if the following occurs within 12 weeks:

- AEs do not recover to \leq grade 1 or baseline
- The dose of steroids (for the management of irAEs) is > 10 mg/day prednisone or equivalent (or as indicated in the tables below)

The 12 weeks' period starts from the time an irAE reaches a severity grade that requires PDR001 interruption.

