Grade 2: Creatinine >1.5 to ≤3 x ULN	
 • Monitor creatinine every 2 to 3 days • Initiate 0.5 to 1 mg/kg/day prednisone equivalents • If worsening or no improvement: 1 to 2 mg/kg/day prednisone equivalents • Consult with specialist and consider renal biopsy 	
 • Interrupt PDR001 until serum creatinine recovers to ≤ Grade 1 or baseline. 
 • Once recovered restart PDR001 treatment at the same dose and schedule 
AE resolution to ≤ Grade 1 must occur within a period of 12 weeks since Grade 2 event has been identified, otherwise PDR001 must be permanently discontinued.

Grade 3: Creatinine >3.0 to ≤6 x ULN	
 • Monitor creatinine every 1 to 2 days • Start 1 to 2 mg/kg/day prednisone equivalents • Consult with nephrologist 	
1st occurrence:
 
 • Interrupt PDR001 until serum creatinine recovers to ≤Grade 1 or baseline. 
 • Once recovered restart PDR001 treatment at the same dose and schedule 
AE resolution to ≤ Grade 1 or baseline must occur within a period of 12 weeks since the Grade 3 event has been identified, otherwise PDR001 must be permanently discontinued
 
2nd occurrence: Permanently discontinue PDR001.

Grade 4: Creatinine >6x ULN	
 • Monitor creatinine daily • Initiate steroids with 1 to 2 mg/kg/day prednisone or equivalent • Consult with nephrologist and consider renal biopsy 	Permanently discontinue PDR001

Table 6-6 Mandatory dose modification requirements and recommended clinical management guidelines for potential immune-related pneumonitis

Pneumonitis (NCI-CTCAE v4.03)		
Grade	Recommended Adverse Event management guidelines	Mandatory Dose Modification requirements
Grade 1: Radiographic changes only- Asymptomatic	
 • CT scan (high-resolution with lung windows) recommended, with serial imaging to monitor for resolution or progression- re-image at least every 3 weeks • Monitor for symptoms every 2-3 days - Clinical evaluation and laboratory work- 	
 • Interrupt PDR001 until recovery to baseline. 
 • Once recovered, restart PDR001 treatment at the same dose and schedule 
If worsens, treat as Grade 2 or 3-4.

Pneumonitis (NCI-CTCAE v4.03)		

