Grade	Recommended Adverse Event management guidelines	Mandatory Dose Modification requirements
	
 up for infection Monitoring of oxygenation via pulse oximetry recommended Consultation of pulmonologist recommended 	AE resolution to ≤ Grade 1 or baseline must occur within a period of 12 weeks since Grade 1 event has been identified, otherwise PDR001 must be permanently discontinued
Grade 2: Symptomatic-medical intervention indicated; limits instrumental ADLs	
 CT scan (high-resolution with lung windows) Monitor symptoms daily, consider hospitalization Clinical evaluation and laboratory work up for infection Consult pulmonologist Pulmonary function tests - if normal at baseline, repeat every 8 weeks Bronchoscopy with biopsy and/or BAL recommended Symptomatic therapy including corticosteroids if clinically indicated (systemic corticosteroids at a dose of 1 to 2 mg/kg/day prednisone or equivalent as clinically indicated). 	
1st occurrence:
 
 Interrupt PDR001 until recovery to Grade ≤1 or baseline 
 Once recovered restart PDR001 treatment at the same dose and schedule 
AE resolution to ≤ Grade 1 or baseline must occur within a period of 12 weeks since Grade 2 event has been identified, otherwise PDR001 must be permanently discontinued.
 
If worsens treat as Grade 3 or 4
 
2nd occurrence: Permanently discontinue PDR001 treatment

Grade 3: Severe symptoms; limits self-care ADLs; oxygen indicated	
 CT scan (high-resolution with lung windows) Clinical evaluation and laboratory work-up for infection Consult pulmonologist 	Permanently discontinue PDR001
Grade 4: Life-threatening respiratory compromise	
 Pulmonary function tests-if < normal, repeat every 8 weeks until ≥ normal Bronchoscopy with biopsy and/or BAL if possible Treat with intravenous steroids (methylprednisolone 125 mg) as indicated. When symptoms improve to ≤ Grade 1, a high dose oral steroid (prednisone 1 to 2 mg/kg once per day or dexamethasone 4 mg every 4 hours). If IV steroids followed by high dose oral steroids does not reduce initial symptoms within 48 to 72 hours, consider non-corticosteroid immunosuppressive medication. 	

Table 6-7 Mandatory dose modification requirements and recommended clinical management guidelines for potential immune-related encephalitis

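### For pneumonitis that persists at Grade 1, the 12-week stop clause in Table 6-6 has no effect, and the patient's disposition at week 12 is not explicit

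*Protocol*

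**What the plan says.** Table 6-6 in protocol Section 6.3.1.2 defines the row as "Grade 1: Radiographic changes only- Asymptomatic". Its dose-modification cell, which Section 6.3.1.2.1 makes mandatory, contains three instructions:

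- Hold and restart: "Interrupt PDR001 until recovery to baseline", with restart at the same dose and schedule once recovered.
- Worsening: "If worsens, treat as Grade 2 or 3-4".
- Deadline: "AE resolution to ≤ Grade 1 or baseline must occur within a period of 12 weeks since Grade 1 event has been identified". The cell gives the consequence of missing this deadline as "otherwise PDR001 must be permanently discontinued".

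The Grade 2 row of the same table says, for a first occurrence, "Interrupt PDR001 until recovery to Grade ≤1 or baseline". Its 12-week deadline uses that same endpoint and counts from identification of the Grade 2 event.

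Two general provisions also bear on the point. Section 6.3.1.1 requires permanent discontinuation when a suspected event has not recovered to Grade 1 or lower, or to baseline, within 12 weeks. It dates the clock as follows: "The 12 weeks' period starts from the time an irAE reaches a severity grade that requires PDR001 interruption". Section 6.1.1 says "The dose may be interrupted for up to 12 weeks" and gives no consequence for reaching that limit.

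**The concern.** One mandatory cell uses two recovery endpoints. The restart sentence accepts only baseline. The discontinuation sentence accepts baseline or any state at Grade 1 or lower, and every event that enters this row is already at Grade 1. A deadline that ends in permanent discontinuation is presumably meant to be able to operate, and for an event that stays at Grade 1 it cannot.

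At stake is consistent handling of a patient whose radiographic change has not cleared by week 12. Pneumonitis is a listed adverse event of special interest (Section 8.1.3), and Section 2.5 notes that fatal immune-related events have been reported with checkpoint inhibitors. Low-grade lung events are not hypothetical for this drug: the study in Japanese patients summarised in Section 1.2.1.2 reports one Grade 1 interstitial pneumonia, suspected to be related to treatment, among 18 patients treated. Sites faced with such a patient at week 12 could reach different decisions and each believe they were following the table.

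**Working it through.** There is no figure in the plan to reproduce and no arithmetic to do. The check is whether the clause can operate for each course that an event in the Grade 1 row can take.

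| Course of the event | Restart condition (baseline) | 12-week condition (Grade 1 or lower, or baseline) | Result |
|---|---|---|---|
| Returns to baseline within 12 weeks | Met | Met | Restart; no stop |
| Stays at Grade 1 | Not met | Met from the day of identification | No restart; no stop under this clause |
| Worsens | Row redirects the event | Row redirects the event | Handled under the Grade 2 or Grade 3–4 row |

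In the second course the same event counts as resolved for the stop clause and as not recovered for restart.

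**Position at week 12 in the second course.** Three provisions apply together:

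1. Restart is barred, because baseline has not been reached (Table 6-6, Grade 1 row).
2. Interruption is limited to 12 weeks, with no stated consequence (Section 6.1.1).
3. The permanent-stop clause is not triggered (Table 6-6, Grade 1 row).

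None of the three says what the patient's status is.

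**Does the general rule resolve it?** No. Under Section 6.3.1.1 the clock starts when the event reaches a grade that requires interruption. For pneumonitis that is Grade 1, so the clock starts with the event, as in the table. The recovery endpoint is also the same, so a persistent Grade 1 event satisfies it from the start. The steroid-dose condition in that section is a separate test and could lead to discontinuation on its own terms, but it does not make the resolution test work.

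**Is the difference in endpoints a pattern of the protocol?** It does not look like one. In the Grade 2 pneumonitis row the restart and deadline endpoints coincide. They also coincide in the Grade 3 rash row (Table 6-4), the Grade 3 nephritis row (Table 6-5) and the Grade 2 encephalitis row (Table 6-7). In those rows the event starts above Grade 1, so a deadline of Grade 1 or lower has content. The Grade 1 pneumonitis row carries the same deadline over to an event that starts at Grade 1.

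A related overlap occurs in Table 6-10. A Grade 1 event that does not improve with symptomatic treatment is to be interrupted until it reaches Grade 1 or lower, or baseline, which it has already done.

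**The case against.** The strongest reply is that the two sentences govern different decisions and can both be obeyed. One sets when drug may resume and the other when it must end for good, and up to week 12 a site can follow both by keeping the patient on hold. That is correct. A reader might infer that the row gives two instructions that cannot both be followed; the documents do not support that. The defect is a mismatch of endpoints that leaves one clause without effect.

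A second reply is that the safety consequence is limited. This also stands. A reader might infer that patients with unresolved pneumonitis could be re-dosed, or that the row offers no protection. It does protect: the interruption applies in full, so an unresolved patient receives no drug. The row covers asymptomatic change, recommends repeat imaging at least every 3 weeks and symptom checks every 2–3 days, and sends worsening events to stricter rows.

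A third reply is that Section 6.1.1 supplies the answer, since a patient who may neither restart nor remain interrupted must be finished with treatment. That is a reasonable inference, and for that reason it would be too strong to say that no path exists at week 12. But Section 6.1.1 does not state discontinuation, whereas the table does so when it means it. Investigator discretion (Section 7.1.5) and the invitation to discuss cases with the sponsor (Section 6.3.1.2.1) allow case-by-case handling but do not replace a mandatory rule.

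Finally, a reader might conclude that the clause can never trigger for anyone. That goes too far. Read literally, an event identified at Grade 1 that worsens and is still at Grade 2 twelve weeks after the Grade 1 date would fail the clause. The row's own instruction moves such an event to the Grade 2 row, with its own clock, but the text does not say that the Grade 1 deadline then lapses.

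**Conclusion.** The point holds for events that persist at Grade 1 and are handled under the Grade 1 row. For these, the 12-week discontinuation clause is met at identification and has no effect, and disposition at week 12 has to be inferred.

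The conclusion rests on reading Grade 1 or lower as including Grade 1, and on the worsening instruction moving an event out of the row. How many patients this touches cannot be stated: the documents give no rate of Grade 1 pneumonitis in this trial and none for its persistence beyond 12 weeks. The reach is limited in any case. Recruitment closed with 116 patients and no more will be enrolled, so only those still on PDR001 are concerned, though treatment may continue after the 10-Aug-2018 cut-off. Sample size, the primary endpoint and the primary analysis are unaffected.

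**What to change.** The sponsor's clinical team should reconcile the restart endpoint and the 12-week endpoint in the Grade 1 row of Table 6-6. The row should then be reconciled with the interruption limit in Section 6.1.1 and the general rule in Section 6.3.1.1, so that the status at week 12 of a patient whose event remains at Grade 1 can be read directly from the protocol. The text should also say whether the Grade 1 deadline still applies once an event has moved to another row. The Grade 1 wording in Table 6-10 could be checked at the same time. Which endpoint or consequence applies is a clinical decision, and none is proposed here.

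The cost is a wording change in one table cell and a consistency check against two short sections. Section 12.1 requires a written, approved amendment for any change to the protocol. No data collection, analysis or SAP text needs to change.
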